We are proposing a prospective, randomized, two-arm, open label pilot study to demonstrate the in vivo effects previously seen in preclinical studies using cervical cancer cell lines16-20. Study participants will be recruited from the Grady Cancer Center of Excellence and the Infectious Disease Program at Grady's Ponce Clinic. A convenience sample of 40 HIV uninfected and infected participants with biopsy-proven HSIL will be randomized to one of two arms (2000 mg of curcumin powder in capsules or placebo inserted intravaginally weekly at bedtime for 12 weeks, (excluding the time when they are on their menses) as demonstrated in the schema.

Cervical cytology, vaginal swabs, colposcopies and biopsies will be performed every 4 weeks during each study visit for the study duration for the primary objectives outlined in specific aims 1-3. These time points were selected to acquire cervical samples prior to treatment, during treatment and 4 weeks after treatment completion (LEEP specimen). Study drug and placebo will be administered during weeks 1-12 (12 weeks of treatment) and no treatment will be administered during weeks 13-16 (washout period). Cervical biopsies will be performed in areas with a colposcopic suggestion of HSIL disease and four additional cervical punch biopsies (one specimen from each of four quadrants) of the cervix will be done for downstream biomarker analysis. The laboratory, pathology and data analysis staff will be blinded to treatment arm. The clinicians performing the colposcopies nor the participants will not be blinded secondary to the evident color of curcumin.

Study Population

HIV uninfected and infected women will be recruited for this study. We will focus only on HIV infected women without an AIDS defining disease, given that the risk of progression from high grade lesions to invasive carcinoma is faster in HIV infected subjects who are significantly immune compromised.

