- J. Optional: If the consent, attend a 2-3 hour focus group (maximum of 20 individuals will be selected for) at the end of the study which will be conducted by [name]. This Focus Group session aims to discuss the acceptability of the product as a treatment for pre-invasive disease using the.

Costs for this study are covered by the study and this includes the associated procedures which are covered by effort by the PI and others listed on the study.

Partners of subjects enrolled in this study

As part of the study, enrolled subjects will be given a partner notification letter informing them on the study, the purpose of this study, route of administration of the capsules, that oral sex is not permitted, and the importance of using condoms for vaginal sex whilst their partner is on the study. The notification letter will also indicate that, male partners may see a temporary discoloration and irritation on their male genetilia if a condom is not used.

Assessment of Compliance

Compliance with weekly intravaginal curcumin/placebo capsules for the duration of the study is measured by the number of nights of reported use as tabulated in the study pill diary.

Endpoints

Subjects will be monitored during the trial for disease progression, adverse events, tolerability and compliance. All study participants will undergo definitive excisional treatment (LEEP) at week 16 of the study period after a 4 weeks washout period. In addition to histology the LEEP specimens will also be tested for biomarkers and curcumin levels.

Samples:

At each visit, cervical biopsies will be divided and sent (1) to pathology for p16 staining to determine the level of dysplasia and grading/documentation of disease and (2) storage for use at a later date for research purposes only. We have designated pathologists, collaborating on this study to ensure standardization of evaluating and grading tissue and other proposed biomarkers.

SCHEDULE OF EVENTS

| Event | | | | | |
|--|--------------------|-------------------|------------------------|-------------------|--------------------|
| | Screening Visit | Baseline Visit | Study Visit Wk 4, 8 | Study Visit 12 | Study Vis Wk 16 |
| Informed Consent | * | | | | |
| Urine pregnancy test | * | * | * | * | * |
| HIV test if status is unknown* | * | | | | |
| Full physical exam | * | | | | |
| Colposcopy with Pap | * | * | * | * | * |
| Pelvic exam | | * | * | * | * |
| Vaginal sampling with colposcopy | | * | * | * | * |

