- Primary endpoints: Human papillomavirus E6/E7 (HPV E6/E7)
- Secondary endpoints: NF-κB, p16INK4a, Rb, p53 and VEGF.

HPV E6/E7 mRNA testing has been demonstrated to be a useful tool in the diagnosis of cervical cancer prevention and will be the primary end-point for this aim. The primary objective for this study is to look at the association between curcumin and cervical disease. In vitro work shows that curcumin treatment inhibits the transcription of HPV E6/E7, thus restoring the expression of proteins such as p53 and that over expression of HPV E6/E7 is a good indicator of risk and progression to cancer. (Maher DM, 2011 Jan;50(1)). Collectively the vitro and our in vivo findings may show that curcumin should be considered an effective chemopreventive and therapeutic agent for cervical cancer prevention and treatment.

Aim2: To quantify levels of curcumin in the cervix of women in the curcumin treatment arm. The mean tissue concentration of curcumin in the cervix at each time point (baseline, 1,2,3,4, and 5 months) will be calculated. This secondary objective quantifies the pharmacologically active levels of curcumin recovered from cervical tissue, for information to be gathered on the levels of curcumin that is absorbed into the cervical tissue and thus eliciting a direct pharmacological effect.

Aim 3: To determine the association between curcumin and other known biomarkers of cervical disease. This exploratory aim seeks to use repeated-measures analyses, utilizing a linear mixed model for the curcumin group to assess the association between and each biomarker (NF-kB, p16INK4a, Rb, p53 and VEGF) and the concentration of curcumin at each time point (baseline, 1, 2, 3, 4, and 5 months).

The primary analysis will be conducted with a two sample two sided t-test to compare the each of the primary endpoints and secondary endpoints, between the two arms of the study, those on treatment (curcumin capsules) and those on the placebo, respectively. If normality cannot be assumed a Wilcoxon rank-sum test will be used instead. Chi-square test or Fisher's exact test will be used to compare categorical characteristics by treatment group.

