In the secondary analyses, for the biomarker measurements, analyses of repeated measures methods are needed to properly account for the correlation between multiple observations from the same subject. Mixed-effects linear models will be employed to analyze such data while adjusting for covariates. Inference from such analyses will be limited by the small sample size of the study. However these data will provide important estimates of within-and between-subject variance that will be helpful for planning future studies. Repeated-measures analyses using mixed linear models will be performed for each biomarker outcome variable (E6/E7, p16INK4a, p53, Rb NF-kB, and VEGF). Each outcome will be analyzed with a means model with SAS Proc Mixed (version 9) providing separate estimates of the means by treatment group (curcumin and placebo) and time on study (baseline, 1,2,3,4, and 5 months). An unstructured variance-covariance form among the repeated measurements will be assumed for each outcome and estimates of the standard errors of parameters will be used to perform statistical tests and

construct 95% confidence intervals. The model-based means are unbiased with unbalanced and missing data, so long as the missing data are non- informative (missing at random). A p-value \leq 0.05 will be considered statistically significant for the main effects (treatment and time on study) and interaction term (treatment group by time on study) from the repeated measures analysis for each outcome. If there is a significant interaction effect then separate comparisons between the two treatment groups will be performed at each time point (baseline and 1,2,3,4, and 5 months). Results from these models will focus on the magnitude of the differences for each outcome. Data will be summarized using adjusted means plus 95% confidence intervals and observed differences plus 95% confidence intervals.

Additionally these biomarkers will also be quantified using immunohistochemistry methods. Immunostaining of p16 (NK4a) will be done and defined as moderate to strong diffuse or focal staining. This characterization of the staining pattern and intensity will allow one to evaluate the histological sample/biposy as having a negative, focal/patchy, or diffuse staining pattern. Generally, 100% of the low-grade and high-grade SIL's are positive for p16 staining and a strong diffuse staining with p16 suggests a high association with high-risk HPV associated lesions.

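### The secondary mixed models count the pre-dose baseline as an outcome visit, which shrinks the treatment main effect to at most 0.80 of a constant effect; they also list a month 5 with no visit, and E6/E7 is left out of the concentration model.

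*Combined protocol and SAP*

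**What the plan says.** The secondary analyses under STATISTICAL ANALYSIS use a mixed model for each of six biomarkers, including E6/E7. The model gives "separate estimates of the means by treatment group (curcumin and placebo) and time on study (baseline, 1,2,3,4, and 5 months"). A p-value of 0.05 or less "will be considered statistically significant for the main effects (treatment and time on study) and interaction term (treatment group by time on study"). By-visit comparisons are conditional: "If there is a significant interaction effect then separate comparisons between the two treatment groups will be performed at each time point", and the list of time points that follows includes baseline. The covariance is specified as follows: "An unstructured variance-covariance form among the repeated measurements will be assumed for each outcome". No degrees-of-freedom method is named. Covariate adjustment is mentioned, but no covariate is named. On reporting, the section says: "Results from these models will focus on the magnitude of the differences for each outcome".

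On timing, RESEARCH DESIGN AND METHODS says: "These time points were selected to acquire cervical samples prior to treatment, during treatment and 4 weeks after treatment completion (LEEP specimen"). The Endpoints section says: "All study participants will undergo definitive excisional treatment (LEEP) at week 16 of the study period after a 4 weeks washout period". The SCHEDULE OF EVENTS has screening, baseline and weeks 4, 8, 12 and 16, and first dispenses study drug at the baseline visit. Aim 2 nevertheless states: "The mean tissue concentration of curcumin in the cervix at each time point (baseline, 1,2,3,4, and 5 months) will be calculated". Aim 3 uses the same six time points.

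The Aim 3 model relates tissue curcumin to NF-κB, p16INK4a, Rb, p53 and VEGF. E6/E7 is not listed. The text before RATIONALE names E6 and E7 mRNA among the molecular targets to be related to tissue concentration, and the hypothesis under SPECIFIC AIMS expects the fall in HPV oncogenic biomarkers to correlate with tissue curcumin.

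**The concern.** There are four points.

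1. **Baseline as an outcome level.** In an arm-by-time means model the treatment main effect is the average of the arm differences over all time levels. One of those levels is pre-dose, where the expected difference is zero, and another follows four weeks off drug. A section that promises to focus on magnitude would thus have a shrunken figure as its only single treatment estimate. The undiluted by-visit contrasts are formally compared only if the interaction is significant. One of them is a baseline test, where any difference is due to chance.
2. **Month 5.** No sampling visit exists for it, so that level has no data.
3. **Small sample.** An unstructured covariance over five visits has 15 parameters, estimated from 40 women. Without a correction the multi-degree-of-freedom tests (time, interaction) can exceed 5%, and the interaction test controls access to the by-visit comparisons.
4. **E6/E7 against tissue curcumin.** The stated hypothesis has no planned test for the primary biomarker.

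The data are meant to inform a larger phase 2 trial, so a diluted effect could be carried into its design.

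**Working it through.** **Inputs.** From Power and sample size calculation: 20 per arm, ratio 1.536, CV 0.5, two-sided 0.05, at least 80% power. From the schedule: five sampling visits with baseline pre-dose, and week 16 off drug. Assumed, because the documents give no figure: log-scale analysis, equal variances, one common correlation ρ between visits (0.3, 0.5 or 0.7), and complete data.

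**The plan's own figure.** Log SD σ = √ln(1 + 0.5²) = 0.472; effect δ = ln 1.536 = 0.429. The two-sample t-test with 38 df has power 0.7995, which reproduces the stated 80%.

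**Share of the effect kept by the main effect.**
- Effect constant over weeks 4 to 16: (0+1+1+1+1)/5 = 0.80, so the ratio appears as exp(0.80 × 0.429) = 1.41.
- Effect gone at week 16: (0+1+1+1+0)/5 = 0.60, so the ratio appears as exp(0.60 × 0.429) = 1.29.
- All six listed levels taken literally: 5/6 = 0.83, but month 5 has no data.

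These shares do not depend on ρ.

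**Power formulas.**
- Main effect: t-test on each woman's five-visit mean, variance σ²(1+4ρ)/5, 38 df, effect 0.80δ or 0.60δ.
- Weeks 4 to 12 average: variance σ²(1+2ρ)/3. With baseline as covariate, subtract ρ²σ² and use 37 df.
- Interaction: noncentral F(4, 35) on changes from baseline (Hotelling).
- Either-test rates, and week 12 both conditional and covariate-adjusted: 20,000 simulated trials per cell, with the exact interaction test as the condition.

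| Power at ρ = 0.3 / 0.5 / 0.7 | Effect persists | Gone at week 16 |
|---|---|---|
| Main effect | 0.92 / 0.82 / 0.73 | 0.72 / 0.58 / 0.49 |
| Interaction | 0.62 / 0.79 / 0.96 | 0.82 / 0.93 / >0.99 |
| Main effect or interaction | 0.97 / 0.96 / 0.99 | 0.95 / 0.97 / >0.99 |
| Week 12 significant, and only after a significant interaction | 0.50 / 0.64 / 0.76 | 0.67 / 0.76 / 0.79 |

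For comparison, the following do not depend on what happens at week 16:
- Week 12 without the condition: 0.80; with baseline as covariate: 0.83 / 0.89 / 0.97.
- Weeks 4 to 12 average: 0.97 / 0.93 / 0.88; with baseline as covariate: 0.99 / 0.99 / >0.99.

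**False positives.** With no effect, the main effect or the interaction is significant in 9% to 10% of trials, or 11% to 12% if the interaction is uncorrected. The size of the uncorrected interaction test is P(T²/4 > F(0.95; 4, 38)) = 0.0675. With complete data the main effect and single-visit contrasts are exact.

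**E6/E7 against concentration.** With 20 women (Fisher z), 80% power needs a between-woman correlation of tanh((1.96 + 0.84)/√17) = 0.59. The 95% interval around zero is about ±tanh(1.96/√17) = ±0.44.

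**The case against.** The best defence is that the plan never names the main effect as its reported estimate. The model yields means by arm and visit, and the summary of adjusted means and observed differences with 95% intervals is not tied to the interaction; only the separate comparisons are. With baseline as a response, the interaction is the natural treatment test and is not diluted. Baseline as an outcome level is not wrong in itself. The plan also has an unconditional two-sample t-test for every biomarker, and either mixed-model test detects the effect in at least 0.95 of trials under the assumptions above. The section admits limited inference, the 6.7% size is a small excess, month 5 is clerical, and Aim 3 is worded as covering other biomarkers.

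Much of this stands and limits the severity. It does not remove the point. The main effect is declared as a test at 0.05, and no alternative single estimate is named. The interaction gives no single treatment estimate, and using both tests roughly doubles the false-positive rate. Baseline as a response is sound if the arms share one baseline mean or a post-baseline contrast is stated; the plan does neither, and its unnamed covariates do not supply it. The scope of Aim 3 may explain the absence of E6/E7, but no other analysis fills the gap.

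The power figures do rest on assumed correlations, and week 12 and the weeks 4 to 12 average are choices made here, since the documents name no key visit. The 0.80 share and the mismatches in the text need none of the correlation assumptions.

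**Conclusion.** The concern holds and should be corrected, but it does not threaten the primary analysis. The main effect keeps at most 0.80 of an effect that is constant after baseline (1.536 appears as 1.41), and 0.60 if the effect is lost by week 16 (1.29). This takes the usual equally weighted main effect in a model with interaction. The loss lies mainly in estimation and in access to the by-visit comparisons. Detection by one test or the other stays high, at the price of a 9% to 10% null rate. Month 5 is a specification error that changes no test on the visits that exist. The missing correction is a small fault. The missing E6/E7 concentration analysis is a real gap between the hypothesis and the plan, although 20 women can support only an estimate with an interval. Confidence is high for the shares and the textual contradictions; the power figures are conditional on the stated assumptions.

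**What to change.** - List the time points as baseline and weeks 4, 8, 12 and 16 in Aim 2, Aim 3 and the mixed models.
- Use baseline as a covariate, or constrain the two arms to a common baseline mean, and drop the between-arm test at baseline.
- Report the week 12 contrast and the weeks 4 to 12 average with 95% intervals whatever the interaction p-value, and report week 16 (washout) separately.
- Name Kenward-Roger degrees of freedom.
- Add E6/E7 to the Aim 3 concentration model with visit as a factor. Pre-dose concentration should be nil in every woman, so without that factor concentration would partly stand in for time. Report the result as an estimate with its interval.

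The cost is SAP wording and a few lines of model code. E6/E7 and tissue curcumin are already to be measured, so no samples are added. The small-sample correction will slightly widen some intervals.

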Acceptability Questionnaires: Descriptive statistics on subject and partner responses from the acceptability questionnaires will be reported.

Power and sample size calculation: The expression of E6/7 is the primary endpoint of the study and will be used in the power and sample size calculation with a two sample two sided t-test. In this study, we will enroll 20 patients in each of the two groups. Therefore, the group sample sizes of 20 in Curcumin group and 20 in placebo group will achieve at least 80% power at the significant level of 0.05 to detect a difference of a ratio of 1.536 or higher in the expression of E6/ between the two groups, assuming the coefficent of variation is 0.5.

SAFETY EVALUATION:

Adverse Events (AEs) and Serious Adverse Events (SAEs)

This investigational agent is studied under IND # 103496 and monitoring will be performed per previously agreed upon FDA guidance.

There may be some minor irritation from the intravaginal curcumin to the vaginal mucosa and staining of underwear. Other side effects which can happen include the upset stomach, diarrhea, burning sensation in the vagina, dizziness, insomnia, rash, pruritus generalized, and fever. The literature shows that over 13 subjects in United States and 151 subjects in India (10) have been studied with curcumin without any serious adverse effects.

Our phase I study has shown that curcumin is safe in dosage up to 2000mg.

Any patient intervention related adverse effects, an unanticipated problem, or reportable protocol deviation/ non-compliance will be reported to the Emory IRB office according to IRB P & P and to the FDA according to regulations.

Any serious adverse effects will be communicated by the principal investigator to the Emory IRB using the standard adverse event reporting forms.

SAEs will be defined per FDA standards and include those that result in death, are life threatening, result in a disability, cause for hospitalization, or to a congenital abnormality or birth effect. SAEs will be reported to the DSMC, IRB and FDA and manufacturer as required.

CLINCAL OUTCOMES AND MEASURES:

The table below gives the descriptions to be used to document findings during colposcopy.

| Colposcopic findings | | | | Presence | |
|----------------------|----------------------|----------------------|----------------------|----------|--------|
| | Grade 1 | Grade 2 | Grade 3 | | |
| | (Mild) | (Moderate) | (Severe) | Present | Absent |

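### The secondary time and treatment-by-time tests use an unstructured covariance in 40 women with no small-sample correction named; without one, the nominal 5% interaction test runs at about 6.7% with the five scheduled visits

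*Combined protocol and SAP*

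**What the plan says.** STATISTICAL ANALYSIS makes a two-sample t-test (or Wilcoxon test) the primary analysis and places the mixed models under secondary analyses. For the latter it is specific on most points:

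- Model: "Each outcome will be analyzed with a means model with SAS Proc Mixed (version 9"), with separate means by arm and "time on study (baseline, 1,2,3,4, and 5 months").
- Covariance: "An unstructured variance-covariance form among the repeated measurements will be assumed for each outcome".
- Inference: "estimates of the standard errors of parameters will be used to perform statistical tests and" to construct 95% confidence intervals.
- Threshold: p ≤ 0.05 for treatment, time and their interaction, separately for E6/E7, p16INK4a, p53, Rb, NF-κB and VEGF.
- Gate: "If there is a significant interaction effect then separate comparisons between the two treatment groups will be performed at each time point".
- Caveat: "Inference from such analyses will be limited by the small sample size of the study".

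The power section gives the size: "we will enroll 20 patients in each of the two groups". The Schedule of Events has sampling at baseline and weeks 4, 8, 12 and 16, and the Endpoints section says: "All study participants will undergo definitive excisional treatment (LEEP) at week 16 of the study period". No visit is scheduled at month 5. No denominator-df method, small-sample adjustment or fallback covariance appears anywhere in the document.

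**The concern.** An unstructured covariance has T(T+1)/2 parameters: 15 for five time points and 21 for six. They are estimated from 40 women. A Wald F test on several contrasts that treats this estimated matrix as known has too small a critical value, so it rejects too often when curcumin does nothing. The treatment-by-time test is one such test, and it decides whether the arms are compared visit by visit. The time main effect is another.

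The plan's caveat about sample size does not cover this. A reader takes a small sample to mean low power and wide intervals, not an excess of false positives. The choice matters somewhat here because the protocol ties its exploratory aim to finding the most relevant duration of treatment, which is a treatment-by-time question.

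**Working it through.** **Inputs.** 20 women per arm (power section). Six time points in the model (STATISTICAL ANALYSIS), five in the Schedule of Events. Nominal level 0.05. Two assumptions are not in the documents: 38 denominator df (40 − 2, the between-subject value), and complete data, since no drop-out rate is given.

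**The plan's own figure.** The only operating characteristic stated is for the t-test: at least 80% power for a ratio of 1.536 with a coefficient of variation of 0.5. On the log scale SD = √ln(1 + 0.5²) = 0.472 and the difference is ln 1.536 = 0.429. The noncentrality is 0.429 / (0.472 × √(2/20)) = 2.87, and the noncentral t with 38 df gives 79.95%. The figure reproduces. It does not involve the mixed model.

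**Exact size of the interaction test.** With complete data, the interaction Wald statistic under an unstructured REML fit is Hotelling's T² on q = T − 1 contrasts with 38 error df. Under the null hypothesis:

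T²/q ~ [38 / (39 − q)] × F(q, 39 − q)

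The uncorrected rule rejects when T²/q exceeds the 95% point of F(q, 38). The true size is therefore P[F(q, 39 − q) > F₀.₉₅(q, 38) × (39 − q)/38].

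- Five time points, q = 4: critical value 2.619; 2.619 × 35/38 = 2.412; P[F(4, 35) > 2.412] = **6.7%**.
- Six time points, q = 5: critical value 2.463; 2.463 × 34/38 = 2.203; P[F(5, 34) > 2.203] = **7.7%**.

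**Other uncorrected references, 40 women.**

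| Reference | Five time points | Six time points |
|---|---|---|
| F, 38 df | 6.7% | 7.7% |
| F, residual df (190 / 228) | 8.6% | 10.1% |
| Chi-square | 9.1% | 10.7% |

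The 38-df assumption is thus the most favourable of these choices.

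**Incomplete data.** If only 32 women remained, all with complete data (30 df), the size would be 7.3% and 8.5%. Simulated REML fits (5,000 trials per setting, correlation 0.5, monotone drop-out, 38 df, Monte Carlo standard error about 0.4 points) gave 7.4% for six time points without drop-out and about 9% with 10% or 20% drop-out. Five time points with 10% drop-out gave 7.2%, which is not clearly different from 6.7%.

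**Corrected critical values.** The exact 5% point is [38/(39 − q)] × F₀.₉₅(q, 39 − q): 1.0857 × 2.641 = 2.87 for five time points and 1.1176 × 2.494 = 2.79 for six, in place of 2.62 and 2.46.

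**Consequence at the gate.** For one outcome under the null hypothesis (complete data, compound symmetry, 40,000 trials per setting), the chance that the gate opens and at least one visit is significant was:

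| Correlation | Five: uncorrected / exact gate | Six: uncorrected / exact gate |
|---|---|---|
| 0.3 | 4.6% / 3.6% | 5.4% / 3.7% |
| 0.5 | 3.4% / 2.7% | 4.0% / 2.7% |
| 0.7 | 2.2% / 1.7% | 2.8% / 1.9% |

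Over the six outcomes, the expected number of false interaction findings rises from 6 × 0.05 = 0.30 to 6 × 0.067 = 0.40 (five time points) or 6 × 0.077 = 0.46 (six).

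**The case against.** The strongest reply is that the plan does not rule out a correction. Kenward-Roger standard errors are also estimated standard errors, and Proc Mixed offers them. That stands. What the documents show is an option left open, and a reader who infers that the trial's tests will in fact run at 7–8% goes too far. The figures hold only if no correction is applied and only for the df assumed.

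The sponsor can also say that the schedule has five sampling times, so 6.7% is the better supported figure. That stands too: 7.7% needs a month-5 measurement that no visit provides.

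A further reply is that little depends on these tests. The mixed models are labelled secondary, the trial is a 40-woman pilot, and the plan says that results will focus on the size of differences. A reader might infer that the primary result or the treatment effect is compromised. The documents do not support this: the primary analysis is a t-test, and the one-df treatment effect on 38 df is exact with complete data. Single-visit intervals had simulated coverage of about 94–96%. Nor does it follow that false visit-level claims generally exceed 5%. In the settings tried they mostly stayed below it, and the correction lowers them by only about 0.5 to 1.7 points.

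What does not stand is that the caveat about sample size settles the matter. It leaves the 0.05 rule and the gate unchanged. The plan fixes the software, model, covariance and threshold, but not the option that decides whether 5% is met.

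**Conclusion.** The point holds in a conditional and modest form. Followed as written with no small-sample correction, the plan gives an interaction test with a true type I error of about 6.7% at the five scheduled time points, or 7.7% at the six listed. This assumes complete data and 38 denominator df. Residual df or a chi-square reference would give about 8.6% to 10.7%, and drop-out may add to the 38-df figure. The time main effect is a test of the same kind and is affected in the same way. The primary t-test and its power, the one-df treatment effect and the single-visit intervals are essentially unaffected, and few extra false visit-level claims result. It is worth correcting because the remedy is simple and nearly free, and because the choice should be settled before data are seen.

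**What to change.** In the repeated-measures paragraph of STATISTICAL ANALYSIS, state that all mixed-model tests and confidence intervals use the Kenward-Roger adjustment (DDFM=KR in Proc Mixed). Name a simpler covariance structure, also with Kenward-Roger, to be used if the unstructured fit does not converge. Reconcile the time points in the model with the Schedule of Events, because their number sets the numerator df.

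With complete data this restores a size of exactly 5%. It needs no extra women, visits or assays: the cost is one model option and a few sentences in the SAP. It is not entirely free, because the critical value for the interaction rises from 2.62 to 2.87 with five time points (2.46 to 2.79 with six), so that test loses a little power.
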